1.3 Secondary endpoints

The secondary objective is to identify the clinical factors associated with FO during a longitudinal follow up. Secondary outcomes of interest are the central volume status (measured by echocardiography and thoracic BIS in combination with photoplethysmography), BP, the cardiac systolic and diastolic function, CV events, hospitalizations, inflammatory- and nutrition status, and quality of life, between CKD stages 3, 4 and 5.

- 1. *Cardiac function:* Electrocardiography and echocardiography (see point 3.3) will be scheduled at baseline, and at 12 months or at end of study visit.
- Thoracic BIS values: a wearable device from Imec Eindhoven will be used to measure thoracic
 BIS values in combination with photoplethysmography and cardiopulmonary index.
- 3. *Blood pressure:* patients will be asked to take BP measurements at home three times a week twice daily with an automatic BP monitor. Mean arterial pressure corrected for heart

frequency will be calculated. BP measurements can be transmitted to the researcher by use of the local Dharma platform.

- 4. *CV events:* CV events defined as hospitalization for coronary disease, heart failure, stroke or peripheral artery disease will be recorded during follow-up.
- 5. *Hospitalization rate and indication:* hospitalization rate and indication will be listed.
- 6. *Inflammatory- and nutrition status:* CRP, ferritin and albumin will be determined every visit (Table 2). Fat tissue mass and lean tissue mass will be analyzed by BIS measurements.
- 7. *Quality of Life assessment:* SF36 questionnaire will be filled in at baseline and end of study visit.

| Table 2 Overview of | f parameters evaluatir | g kidney function, r | enal metabolism a | and inflammation in HORUZ study. |
|---------------------|------------------------|----------------------|-------------------|----------------------------------|

| Assay | Material | Standard care | Frequency |
|-------------------------|--------------|---------------|-------------------|
| Residual renal function | | | |
| Urea | Plasma/serum | yes | Every study visit |
| Creatinine | | | |
| Metabolism and electrol | ytes | | |
| Hemoglobin | Plasma/serum | yes | Every study visit |
| Sodium | | | |
| Potassium | | | |
| Bicarbonate | | | |
| Phosphate | | | |
| Calcium | | | |
| NT-proBNP | | No | Every study visit |
| Inflammation | | | |
| C-reactive protein | Plasma/serum | yes | Every study visit |
| Leucocytes | | | |
| Albumin | | | |

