IVS = interventricular septum thickness PWT = posterior wall thickness EDD = end diastolic diameter of the left ventricle

LVEF will be calculated using diastolic and systolic LV volumes measured by the single-plane Simpson's

rule method: ((Dvol - Svol)/Dvol) x 100; 0.50 is the cutoff point.

LV geometry is divided into four categories, based on LVMI and RWT:

[figure not shown]

Figure 5 Left ventricle classification system of Koren et al., adapted from Middleton et al.¹⁷

Diastolic dysfunction is defined as an abnormality of diastolic distensibility, filling, or relaxation of the left ventricle, regardless of whether the ejection fraction is normal or abnormal and whether the patient is symptomatic or asymptomatic.⁴⁶

4. Withdrawal of individual subjects

Participants can exit the study at any time for any reason if they wish to do so. The investigator can decide to withdraw a subject from the study for urgent medical reasons. In case of withdrawal, an end of study visit will be scheduled to perform last measurements according to visit 5. As there is no medication intervention in this study, there is no need for a safety procedure during withdrawal. Withdrawals will not be further followed.

5. Replacement of subjects withdrawn from treatment

Patients who withdraw from the study will not be replaced, as this has already been taken into account in the sample size calculation.

6. Premature termination of the study

As the interventions in this study are non-invasive and no medication is used, no specific termination criteria are formulated.

SAFETY REPORTING

1. Temporary halt for reasons of subject safety

The sponsor will suspend the study if there is sufficient ground that continuation of the study will jeopardize subject health or safety. The sponsor will notify the accredited Ethical Committee without undue delay of a temporary halt including the reason for such an action. The study will be suspended pending a further positive decision by the accredited Ethical Committee. The investigator will take care that all subjects are kept informed.

2. Adverse and serious adverse events, SUSARs

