2.3 Suspected unexpected serious adverse reactions (SUSAR)

Not applicable.

3. Follow-up of adverse events

AE according to the study are considered very unlikely, due to the fact that only non-invasive methods are used. All AEs will be followed until a stable situation has been reached and treated to standard procedures.

4. Data Safety Monitoring Board (DSMB)

Not applicable.

STATISTICAL ANALYSIS

A table with baseline characteristics of all subjects will be provided. Baseline characteristics of the population will be expressed as the mean \pm standard deviation if normally distributed, or as the median [25th – 75th percentile] as not normally distributed, for continuous and dichotomous data, and as the frequency (%) for categorical data. Measurements of drop-outs will be included until the moment of withdrawal from the study. Normality in distribution will be tested by the Shapiro-Wilk statistic. Repeated measurements ANOVA techniques will be used for analysis. Pearson's Chi-squared test will be used to assess whether there is any distinction between subgroups in rate of kidney function decline. In case the analysis of the baseline characteristics showed any clinically relevant imbalance, we will also perform a multivariable logistic regression analysis in order to correct for this imbalance. Differences in LVH will be corrected for systolic BP and haemoglobin, as these are predictors of LVH in predialysis population.¹⁵ Depending on the level of measurement a Chi-squared test or a T-test will be used to assess differences in secondary study parameters, and logistic and linear regression for baseline-corrected estimates. Tests will be considered significant if p-values are ≤ 0.05 .

ETHICAL CONSIDERATIONS

1. Regulation statement

The study will be conducted according to the principles of the Declaration of Helsinki (Fortaleza, Brasil, 2013).

2. Recruitment and consent

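### The CV event endpoint has no fatal component and its planned comparison ignores follow-up time, so events are understated in any CKD stage with more early exits

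*Combined protocol and SAP*

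**What the plan says.** Methods 1.3 (Secondary endpoints) lists, among outcomes compared between CKD stages 3, 4 and 5, cardiovascular events and hospitalisations. The event is defined so: "CV events defined as hospitalization for coronary disease, heart failure, stroke or peripheral artery disease will be recorded during follow-up". For hospitalisation, the "hospitalization rate and indication will be listed", with no denominator given.

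The Statistical Analysis section names no method for CV events as such. Its general rule is: "Depending on the level of measurement a Chi-squared test or a T-test will be used to assess differences in secondary study parameters", followed by "logistic and linear regression for baseline-corrected estimates". On incomplete follow-up it says: "Measurements of drop-outs will be included until the moment of withdrawal from the study". Methods 4 (Withdrawal of individual subjects) schedules an end-of-study visit on withdrawal and then states: "Withdrawals will not be further followed". Planned follow-up of CKD patients is 12 months.

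Death appears only as a criterion for a serious adverse event (Safety Reporting 2.2 and the footnote to the registration form). No text links it to the CV endpoint or treats it as a competing event. Time to renal replacement therapy is recorded (Methods 1.2), without an analysis method.

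**The concern.** Two gaps work in the same direction.

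- **Definition.** A patient who dies of a cardiovascular cause outside hospital, with no earlier admission for a listed cause, has no event. The protocol's introduction says that mortality in CKD is driven mainly by cardiovascular comorbidity, so the omitted outcome matters on its own rationale.
- **Analysis.** A proportion with an event, or a mean number of events, depends on how long patients were observed. The plan expects some to leave early and stops observing them when they do, yet none of the named methods uses time at risk.

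If one CKD stage loses more patients or follow-up time than another, its event proportion falls for a reason unrelated to its true rate. A real excess in that stage would look smaller than it is.

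**Working it through.** **The plan's own figures.** The sample size concerns eGFR slope (Methods, Study Population 4), but it is the only source for expected loss. With a difference of 2, SD 4.7, two-sided alpha 0.05 and power 0.80:

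n = 2 × (4.7 × (1.960 + 0.842) / 2)² = 86.7, or 87 per group; the plan states 86, which reproduces to rounding.

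The inflated figure is 103 per group, so the allowance is 103 − 86 = 17, and 17/103 = 16.5%. The plan does not say how losses would split by CKD stage.

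**Model (assumptions).** The event rate r per person-year is constant. One group is complete to 12 months. In the other, a share f leaves uniformly over the year. The documents give no rate, so r runs from 0.05 to 0.30.

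- Complete follow-up: p_F = 1 − exp(−r)
- Leavers, averaged over exit time: p_L = 1 − (1 − exp(−r))/r
- Group with losses: p_M = (1 − f) p_F + f p_L
- False gap = p_F − p_M = f (p_F − p_L)

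**Equal true rates, f = 16.5% in one group, none in the other** (gaps computed before rounding):

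| r | p_F | p_L | p_M | Gap (points) | Crude ratio |
|---|---|---|---|---|---|
| 0.05 | 4.88% | 2.46% | 4.48% | 0.40 | 0.92 |
| 0.10 | 9.52% | 4.84% | 8.74% | 0.77 | 0.92 |
| 0.20 | 18.13% | 9.37% | 16.68% | 1.45 | 0.92 |
| 0.30 | 25.92% | 13.61% | 23.89% | 2.03 | 0.92 |

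A person-time rate ratio is 1.00 throughout. With the same f in both groups the gap is zero.

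**Extreme split.** If both groups' allowances (34 patients) fell in one group of 103, f = 34/103 = 33.0%. At r = 0.30 the gap is 0.330 × (0.2592 − 0.1361) = 4.1 points.

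**True rate ratio 1.5 in the group with losses**, reference rate 0.10 to 0.20. With no loss, the ratio of proportions is 0.1393/0.0952 = 1.46 (reference rate 0.10) to 0.2592/0.1813 = 1.43 (0.20). With 17% loss it is 1.34 to 1.31; with 50% loss, 1.11 to 1.09.

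**Deaths.** If a share q of a group dies of a cardiovascular cause with no qualifying admission, the proportion with CV death or admission is understated by exactly q. The documents give nothing from which to estimate q.

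**The case against.** Much of the case for leaving this alone is fair.

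- **Size.** Any bias from lost exposure is small beside sampling error. With 103 per group and proportions near 23%, the standard error of a difference is √(2 × 0.23 × 0.77 / 103) = 5.9 points, against a false gap of 2.0 points or less in the table. The 103 belongs to the fluid-overload comparison; numbers per CKD stage are not given.
- **Long differences in follow-up.** A reader might picture 9 months' mean follow-up against 12. With uniform exit, mean follow-up is 12 × (1 − f/2), so 9 months needs f = 50% in one group and none in the other. A 16.5% loss gives 11.0 months.
- **Reversal.** A reader might infer that the comparison could change direction. The documents do not show this: at a true ratio of 1.5 the crude ratio stays above 1 even with 50% one-sided loss.
- **Who leaves.** It is tempting to say that stage 5 or fluid-overloaded patients exit through renal replacement therapy. The protocol does not say that starting it ends follow-up, and for these outcomes it names CKD stages, not fluid-overload groups.
- **Wording.** The Chi-squared test is not assigned to CV events by name, and the plan is silent on how deaths are counted. Both follow from the general rule and the definition. The T-test and both regressions share the gap.
- **Legitimacy.** Hospitalisation alone is an acceptable endpoint if deaths are reported beside it, and the withdrawal visit can capture events up to exit.

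These points limit size and certainty. They do not supply a method that uses follow-up time or a rule for fatal events.

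**Conclusion.** The concern holds as a gap in a secondary endpoint. CV deaths without a qualifying admission add no event, and the stated methods understate events in any CKD stage with more early exits; if that stage has the higher true rate, the effect is attenuation. The illustrated false gap is about 0.4 to 2.0 percentage points. It rests on an assumed constant rate of 0.05 to 0.30 per year, uniform exit, and the whole 16.5% loss falling on one side. The contribution of deaths cannot be sized.

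A reader might also infer a comparison of 12 months in patients with one month in healthy controls, because the Objectives mention controls for the secondary outcomes. The controls are, however, described as serving the cross-sectional part, and Methods 1.3 leaves them out of its comparison. Those sections need reconciling, but the conclusion here does not depend on it.

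**What to change.** 1. Define the CV event as CV death or hospitalisation for a listed cause, or keep the present definition and report CV death separately by CKD stage.
2. Compare first events between CKD stages by Kaplan-Meier and Cox, or by cumulative incidence, with censoring at withdrawal or end of follow-up and non-CV death as a competing event. State whether observation continues after renal replacement therapy starts.
3. Compare hospitalisation counts by Poisson or negative binomial regression with log follow-up time as offset.
4. Report follow-up time and reasons for exit by CKD stage. These methods correct for unequal exposure but still assume that withdrawal is unrelated to the risk of an event.

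The cost is a few sentences in Methods 1.3 and the Statistical Analysis section. The legible registration form shows a visit date and one combined column for CV events, hospitalisation and adverse events. Event date and cause of death should be added if they are not already there. Deaths are already reportable as serious adverse events.

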1.1 Demographic and clinical data

The prevalent CKD stage 3 – 5 population will be screened by the researcher. After verification of the in- and exclusion criteria, eligible patients will be invited to participate the HORUZ study, with approval of their treating nephrologist. After signing the informed consent, data at baseline and during followup visits will be collected on paper clinical report forms (Table 1). Hypertension is defined as an office BP \geq 140/90 mmHg or home BP \geq 130/80 mmHg, or current medication for hypertension.¹ Diabetes mellitus will be assumed to be present in patients who report use of insulin and/or oral hypoglycemic agents. CV diseases include coronary artery disease, as documented by coronary angiography or a history of myocardial infarction, congestive heart failure, cerebrovascular accident, or known peripheral vascular disease. Fluid assessments, including BIS measurements, will be recorded on the HORUZ registration form (Appendix).

The healthy controls included for the cross-sectional analysis will only be followed according to visit 0 and 1.

| | Baseline Visit 0 | Month 1 Visit 1 | Month 3 Visit 2 | Month 6 Visit 3 | Month 9 Visit 4 | Month 12/ end of study Visit 5 |
|--|---------------------|--------------------|--------------------|--------------------|--------------------|-----------------------------------|
| Consent | х | | | | | |
| Demographics: Age (y) Gender Height (cm) Smoking status Etiology CKD Hypertension Diabetes CV disease Tx list | x | | | | | |
| eGFR _{creat} | x | x | x | x | x | x |
| CrUrCl | | x | x | x | x | x |
| 24h urine | | x | x | x | x | x |

Table 1 Schedule of the main data to collect in CKD subjects.

| BP | x | | x | x | x | x |
|-----------------|---|---|---|---|---|---|
| ECG | x | | x | x | x | x |
| Echo cor | | x | | | | x |
| CV events | | x | x | x | x | x |
| Hospitalization | | x | x | x | x | x |
| Medication | x | | x | x | x | x |
| Whole body BIS | x | | x | x | x | x |
| Thoracic BIS | x | | x | x | x | x |
| SF36 | x | | | | | x |
| Adverse event | | x | x | x | x | x |

Abbreviations: BIS, bioimpedance spectroscopy; BP, blood pressure; CKD, chronic kidney failure; Creat, creatinine; CrUrCl, mixed creatinine

and urea clearance; CV, cardiovascular; ECG, electrocardiography; M, month; SF36, short form 36 questionnaire; Tx, transplantation.

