| Ferritin | | | |
| 24 urine collection | | | |
| Quantity | Urine | No | Every study visit |
| Creatinine | | | |
| Urea | | | |
| Sodium | | | |
| Albumin | | | |
| Protein | | | |

2. Randomization

Not applicable.

3. Study procedures and interventions

After inclusion during the baseline visit, a research visit will be scheduled every 3 months until end of study or withdrawal. Study visits will be scheduled as much as possible before the regular visit to the treating nephrologist. During this period of follow up, all participants will undergo the following procedures to determine the predefined research parameters (Table 1):

At the first visit, patient's medical file will be checked for baseline demographic information, comorbidities, risk factors and medication use. Patients will be asked about complains or symptoms related to fluid homeostasis (weight gain, shortness of breath, thoracic pressure, palpitations, muscle cramps, dizziness, fatigue, thirst, obstipation). Physical signs of fluid imbalance (subcutaneous edema) will be evaluated by physical examination. Subjects will be requested to collect 24h urine sample and take a blood sample to determine the mixed urea and creatinine clearance. BP, ECG and echocardiography will be performed in all subjects. BIS will be performed by the reference and wearable device. Patients will be asked to fulfill the SF36 questionnaire.

During subsequent visits, anamnesis, physical examination, blood- and urine samples, BP and BIS measurements will be taken from all subjects.

At 3 and 12 months of follow up, additional evaluation of cardiac function and quality of life will be performed.

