3.1 BP measurements

All subjects will be asked to measure BP three times a week, twice a day (morning and evening before sleeping). BP will be measured by an automatically oscillometer. The researcher will evaluate the BP each study visit. A mean value of morning and evening measurements will be calculated.

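### Table 1 schedules no BP or bioimpedance at Visit 1, where it also puts the first echo and first 24h-urine clearance; the text disagrees on both counts

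*Combined protocol and SAP*

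**What the plan says.** Text on BP and BIS:

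- The Summary (Intervention) has both performed at every study visit.
- METHODS, section 3 (Study procedures and interventions) says "During subsequent visits, anamnesis, physical examination, blood- and urine samples, BP and BIS measurements will be taken from all subjects".
- METHODS 3.1 adds, for BP only, "The researcher will evaluate the BP each study visit".

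Table 1 (METHODS 1.1) marks both BIS rows at baseline and from month 3 onwards, with nothing at Visit 1: "Whole body BIS | x | | x | x | x | x" and "Thoracic BIS | x | | x | x | x | x". The BP row has the same pattern.

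The rows for kidney clearance run the other way, starting at Visit 1: "24h urine | | x | x | x | x | x", and likewise CrUrCl. The echo row is marked at Visits 1 and 5 only. The registration form in the Appendix agrees on the echo: its Visit 1 and end-of-study rows carry a field for the echo date, and its Visit 0 row does not.

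The text times the first echo differently. METHODS 1.3 and 3.3 place it at baseline. Section 3 groups echo, BP, BIS and the request for 24h urine and a clearance blood sample at the first visit.

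For controls, METHODS 1.1 states "The healthy controls included for the cross-sectional analysis will only be followed according to visit 0 and 1".

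**The concern.** The table and the text cannot both be followed, and the blank cells fall on the visit where pairing matters most. Two pieces of the plan need BP or fluid status measured close to the echo.

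- The Hypothesis section expects the thoracic BIS signal to predict cardiac function as well as echocardiography does, and the secondary outcome of central volume status uses both methods. Volume status can change within weeks, so a comparison of two methods is cleanest when both are taken at one visit.
- STATISTICAL ANALYSIS states "Differences in LVH will be corrected for systolic BP and haemoglobin". It does not say which BP value (office or home) or from what time relative to the echo. If no BP is scheduled at the echo visit, the analyst must choose between a value from before the echo and one from after it.

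Controls have no visit after Visit 1, so a pair missed in them cannot be made good later.

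**Working it through.** The plan gives no figure for this point, so the check is a cross-tabulation of visit marks.

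**Inputs, from Table 1** (V0 = baseline, V1 = month 1, V2 = month 3, V3 = month 6, V4 = month 9, V5 = month 12):

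| Item | V0 | V1 | V2 | V3 | V4 | V5 |
|---|---|---|---|---|---|---|
| BP | x | – | x | x | x | x |
| Whole-body BIS | x | – | x | x | x | x |
| Thoracic BIS | x | – | x | x | x | x |
| Echo | – | x | – | – | – | x |
| CrUrCl | – | x | x | x | x | x |
| 24h urine | – | x | x | x | x | x |
| eGFR | x | x | x | x | x | x |

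**Visits at which both items are marked**

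- Echo with BP or either BIS, CKD patients: V5 only, out of V1 and V5. Unpaired: 2 − 1 = 1 of 2.
- CrUrCl or 24h urine with BP or either BIS, CKD patients: V2 to V5, out of V1 to V5. Unpaired: 5 − 4 = 1 of 5, and it is the first.
- Controls (V0 and V1 only): echo and clearance at V1, BP and BIS at V0. Paired: 0 of 1 for each.

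**Distance to the nearest value under Table 1**

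- Backward, V1 to V0: 1 − 0 = about 1 month.
- Forward, V1 to V2: 3 − 1 = about 2 months, available in CKD patients only.

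**The same counts under other readings**

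- Text followed throughout (echo, urine, BP and BIS together at the first visit): no unpaired first echo or clearance, in patients or controls.
- Table 1 for echo and urine, but the text for BP and BIS at every visit: again none unpaired.

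The loss therefore runs from none to the figures above, depending on which source the site follows. The full loss needs Table 1 to be followed for all rows.

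**Choice of BP for the LVH correction.** Home readings are asked for three days a week, twice a day: 3 × 2 = 6 per week. Month 3 is about 13 weeks, so 13 × 6 = 78 readings by V2. Month 1 is about 13/3 weeks, so about 26 readings by V1. A home mean formed at V2 over the whole period would have (78 − 26)/78 = 52/78 = 67% of its readings after a V1 echo. Without a stated window, the covariate could come largely from after the outcome.

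**Primary analysis.** BIS is marked at V0, so fluid-overload grouping at baseline is available. eGFR is marked at all six visits, so the slope is unaffected. The sample size uses only a difference of 2 and an SD of 4.7: 2 × (4.7 × (1.960 + 0.842)/2)² = 86.7 per group, against the stated 86. Nothing in it depends on Visit 1.

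**The case against.** The strongest reply is that this may be a drafting slip with no loss of data. Section 3 mentions only three-monthly visits after baseline and no month-1 visit. Its subsequent visits could therefore be read as V2 to V5, where Table 1 does mark BP and BIS, with Visit 1 merely completing the baseline work-up. METHODS 1.2 and Table 2 also have urine collected at every study visit, which would include baseline, where BIS is marked. This reply stands in part: it is why the loss is conditional on Table 1. It does not remove the conflict. The Summary says every visit, section 3.1 says the same for BP, and the registration form supports a Visit 1 echo, so that mark is unlikely to be stray. The form cannot settle the BIS question, because its extracted BIS cells also look empty at Visit 3, where Table 1 requires BIS.

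A second reply is that STATISTICAL ANALYSIS specifies no analysis requiring same-day pairs, and that the baseline office BP could serve for the LVH correction. That is fair: no bias from a one-month gap has been shown. The remaining point is that the plan does not say which value to use.

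A reader might infer three stronger claims that the documents do not support.

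- *The first month of home BP is lost.* Home measurement is not tied to visits, readings can be transmitted by the platform named in METHODS 1.3, and they can be averaged at V2. The form has a home BP column and a Visit 1 row.
- *A planned home BP comparison with controls is lost.* BP is not among the outcomes that the Summary and OBJECTIVES compare with controls. METHODS 1.3 adds BP only for comparison between CKD stages.
- *The text requires medication at Visit 1.* Table 1 does leave it blank ("Medication | x | | x | x | x | x"), but neither section 3 on later visits nor section 3.1 mentions it, so there is no contradiction.

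**Conclusion.** The point holds as an inconsistency in the schedule with consequences for secondary analyses. Table 1 conflicts with the Summary and METHODS sections 3 and 3.1 on BP (and, except in 3.1, on BIS). It also conflicts with METHODS 1.3, 3 and 3.3 on the timing of the first echo, and with section 3 on the first urine and clearance samples.

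If Table 1 governs, 1 of 2 echoes and 1 of 5 clearance visits in CKD patients, and the single echo and clearance in controls, have no same-visit BP or fluid status. If the text governs, nothing is lost.

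The control figure assumes that controls follow the Visit 0 and Visit 1 columns of Table 1 as printed, although its caption refers to CKD subjects. It would be wrong to extend the point to the primary endpoint: the eGFR slope, the baseline fluid-overload grouping and the power are untouched.

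**What to change.** Reconcile Table 1 and the registration form with the Summary and METHODS 1.3, 3, 3.1 and 3.3. Whichever visit is chosen for the first echo and first 24h urine, schedule BP, whole-body BIS and thoracic BIS at that same visit, for CKD subjects and controls. If it stays at Visit 1, mark those three rows at Visit 1. State explicitly that the schedule applies to controls.

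In STATISTICAL ANALYSIS, name the systolic BP used for the LVH correction: office or home, and from which window around the first echo. The window should follow the echo date that is settled on. A mean of readings between Visits 0 and 1, for instance, precedes a Visit 1 echo but follows a baseline one.

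Cost: an edit to one table, one form and one sentence, with no added visit. If the echo stays at Visit 1, that visit lengthens by about 30 minutes. This is an estimate: METHODS 3.2 gives 20 minutes for the thoracic measurement and at least 5 minutes of rest beforehand (20 + 5 = 25), and the whole-body measurement and BP are added. Home BP readings are already being taken, so they add no burden.
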